### 1.1 Eligible Participants:

This is a study of patients

[figure not shown]
- aged 40 to 80 years with
- ASLS defined as
  - lumbar curve with a coronal Cobb measurement  $\geq 30^\circ$ , and
  - **either of the following:**
    - Oswestry Disability Index (ODI) score  $\geq 20$  **or**
    - SRS-QOL score  $\leq 4.0$  in the domains of pain, function and/or appearance.
- **If assigned to surgical intervention** (by randomization or patient preference), the intervention plan would include, at a minimum, the Cobb levels of the Thoracolumbar/lumbar spine.

Patients 81 years or older are not eligible for inclusion, as most providers would not recommend major surgical procedures of this nature for these patients in this age group due to the increased risk of perioperative morbidity and mortality. Eligibility for participation is not restricted based on gender, ethnicity or principle language.

Excluded from participation are patients with any of the following factors:

- Substantial cardiac, pulmonary, renal or metabolic disease that, in the judgment of the surgical team, would preclude performing an operative procedure without undue risk of morbidity and mortality
- Concomitant high-grade spondylolisthesis (Grade  $\geq 3$ )
- Prior thoracic or multiple level lumbar laminectomy or decompression [single or two level lumbar decompression (e.g., herniated disc) will not be an exclusion]
- Prior thoracic or lumbar fusion
- Osteoporosis evidence by a dual-energy x-ray absorptiometry (DEXA) T-score  $<-3.0$  at the femoral neck for patients considered to be at risk (post-menopausal females, males  $\geq 60$  years of age, steroid dependent rheumatoid arthritis, status post organ transplantation, etc.). Patients may be randomized prior to obtaining DEXA results. Non-Surgical patients may initiate non-surgical treatments prior to completion of DEXA (if required) as non-surgical treatments will not affect DEXA results BUT DEXA must be completed and results entered within 3 months of enrollment. Surgical patient must have DEXA prior to surgical intervention. Waivers will be provided for patients meeting inclusion criteria who have had bilateral total hip replacements only if t score of spine and wrist are provided.
- Neuromuscular scoliosis (e.g., spinal muscular atrophy, cerebral palsy, Parkinson's Disease, post-polio syndrome, Charcot Marie Tooth disease)

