- Congenital scoliosis in the lumbar spine. Congenital anomalies of the cervical or thoracic spine are acceptable.
- Spine tumor, infection or connective tissue disorder
- Cognitively impaired or unable/unwilling to comply with follow-up
- Pregnancy or planning on conceiving during time of study involvement
- Ankylosing Spondylitis
- Past history of vertebroplasty or kyphoplasty of the thoracic or lumbar spine

Figure 1: Patient flow and Triage

**1.2 Identification and Enrollment:** Site investigators and/or research coordinators will identify potential study participants based on patient history, physical exam, radiographs and HRQOL scores. See Section 19 Administrative Forms: Screening Checklist. Patients meeting inclusion/exclusion criteria will be offered study participation. Potential patients will view a short video regarding study participation.

Eligible patients not consenting to study participation will be entered into the electronic database in a de-identified manner. Age, gender, inclusion criteria and reason for declining participation will be documented.

**1.3 Randomization and Observational Cohort Assignments:** Patients consenting to randomization will be randomized 1:1 to the non-operative or operative intervention arms. A permuted randomized block approach with blocks of size 4, 6 and 8 and stratified by site, age group (2 levels: 40-59 years of age, 60-80 years of age), gender and Cobb angle-based severity (2 levels: 30-54°, 55-100°) will be used to ensure representative treatment assignment across these demographic and disease-specific categories with approximately balanced assignment totals at interim intervals as well. Based on preliminary data, we anticipate that 57% of participants will be in the younger age category and 43% in the older age category.

Patient loss to follow-up can affect the randomization balance and quality. When a patient is lost to follow-up prior to treatment or because of an administrative error, such as qualifying a patient for inclusion in

the study when, in fact, study inclusion criteria were not met or exclusion criteria were initially missed, these patients will be removed from the study along with all study data. The guidelines for removing a patient from the study will follow the ICH guidelines; subjects who fail to satisfy an entry criterion will be excluded from the analysis under the following circumstances:

1. the entry criterion was measured prior to randomization;

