2. the detection of the relevant eligibility violations can be made completely objectively;
3. all subjects receive equal scrutiny for eligibility violations; and
4. all detected violations of the particular entry criterion are excluded.

The study management plan is explicitly designed to minimize these events. Specifically, there will be electronic registration by site coordinator with explicit inclusion and exclusion criteria assessment on the enrollment form and review of registration by the Project Manager (PM) at Washington University.

In the observational cohort, the choice of nonoperative vs. operative care will be made by the patient guided by the provider's recommendation and presentation of existing data regarding nonoperative and operative care based on the following parameters: Patients with clinical symptoms of pain and functional limitations that are well controlled with non-operative care will be encouraged to pursue nonoperative care. Patients who have not demonstrated access or utilization to previous nonoperative care for their symptoms will be directed to non-operative care as an initial treatment. Enrollments into the observational arms will be closed when each arm's sample size is reached in order to achieve equal numbers of patients in each arm at the conclusion of the study.

**1.4 Study Interventions:** Regardless of study cohort participation (randomized or observational), interventions will not be implemented until the PM has confirmed appropriate enrollment. Nonoperative interventions will then be implemented as soon as possible. Due to the length and complexity of spinal deformity procedures, available dates for elective operative procedures may range from 1 to 6 months. Therefore, operative intervention will take place within six months of treatment assignment but baseline assessments, specifically MD assessment, patient reported HRQOL and treadmill tests must be completed within 6 months prior to intervention. Standardized protocol guidelines for nonoperative and operative treatment, as detailed below, will be followed by all sites.

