**Surgical Summary:** For patients managed operatively, a surgical summary will be completed by the surgeon at the time of intervention. Data captured will include, but not be limited to: blood loss, length of surgery, surgical approach, and vertebral levels involved. Equally important will be the reporting of any intra-operative adverse events, as well perioperative adverse events occurring prior to discharge. Procedural codes (CPT codes) will also be reported.

**Patient Intervention Follow-Up:** All participants will complete a comprehensive description of the nonoperative modalities used, and the frequency of use will be detailed (3, 6, 9, 12, 15, 18, 21, 24, 30, 36, 42, 48, 60 & 72 months post-intervention). These assessments will be part of the standard questionnaires given at each study follow-up. Patient diaries will be used as memory aids but will not be used for primary data collection. Any adverse events stemming from nonoperative or operative treatments will be recorded along with changes in health history.

**Monitored Events:** Sites will complete a Monitored Events Case Report Form (CRF) at each clinical follow-up appointment to report: Serious or Unexpected but reasonably related adverse events (AEs), Crossover to the other intervention, or exiting the study. In addition, sites will complete this form as applicable with each patient contact, including telephone calls.

**Due Diligence Report:** This report will be run by the Project manager after each follow up visit data has been entered into database. The report will calculate differences in previously reported HRQOL value. Any patient with a decrease of -0.5 in the SRS domains or an increase of 10 or more points in the ODI score warrant further investigation.

The primary outcome variable will be the change in SRS-QOL subscore because the literature supports this questionnaire as a more disease-specific tool for assessment of spinal deformities. The concurrent validity of the SRS-QOL function domain compared favorably to the SF-12 PCS ( $r=0.73$ ) and the ODI ( $r=0.87$ ), as did the SRS-QOL mental health domain compared to the SF-12 MCS ( $r=0.87$ ). Thus, the SRS-QOL is especially suited to our study population and research questions. Changes in ODI and SF-12 will also be assessed as they are frequently used measures of QOL and will facilitate comparison of our findings with those of others.

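### Protocol 1.3 removes wrongly entered patients with all their study data, does not limit this to untreated patients, and conflicts with the analysis-only exclusion rule in the same paragraph

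*Protocol*

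**What the plan says.** Protocol 1.3 (Randomization and Observational Cohort Assignments) gives two triggers for removal: "When a patient is lost to follow-up prior to treatment or because of an administrative error". The second covers patients who did not meet inclusion criteria or whose "exclusion criteria were initially missed, these patients will be removed from the study along with all study data".

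The same paragraph then says that removal will follow ICH guidelines and gives a rule with a different consequence: "subjects who fail to satisfy an entry criterion will be excluded from the analysis under the following circumstances". Four conditions follow. The first is that "the entry criterion was measured prior to randomization"; the second is that "the detection of the relevant eligibility violations can be made completely objectively"; the third and fourth require equal scrutiny of all subjects and exclusion of every detected violation of the criterion concerned.

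Other relevant text:

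- Protocol 1.1 allows randomization before DEXA results are available and states: "Non-Surgical patients may initiate non-surgical treatments prior to completion of DEXA (if required"). Results are due within 3 months of enrollment. Surgical patients must have the DEXA before surgery.
- Protocol 1.4 sets a check before treatment: "interventions will not be implemented until the PM has confirmed appropriate enrollment".
- Protocol 1.5.1 collects adverse events on study forms, namely the Surgical Summary and the Monitored Events form. On the former it says: "Equally important will be the reporting of any intra-operative adverse events, as well perioperative adverse events occurring prior to discharge".
- Specific Aim 2, in both documents, makes adverse events an outcome to be related to patient factors and comorbidities in both arms.
- The SAP (Addendum 8/29/12) assigns complications and severe adverse events to intervals counted from the intervention date. It defines no safety population and does not mention removed patients.

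**The concern.** Excluding a wrongly entered patient from an efficacy analysis can be defended under tight conditions. Discarding that patient's data is a different act. Once a study intervention has been given, any harm that followed belongs in the account of that intervention, whether or not the patient should have been entered.

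Three things are at stake. Adverse events in treated patients could be missing from the complication rates. Aim 2 could lose patients from its analysis of comorbidities and adverse events. Patients removed from the study would also leave protocol follow-up. This last is at odds with how the protocol treats others who depart from plan: patients who have surgery elsewhere (end of 1.4.2) or stop treatment at the site (1.5.3) stay in follow-up.

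**Working it through.** The plan states no figure on this point, so the main check is to set the texts side by side.

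**Step 1: does the removal sentence reach treated patients?** The words about timing before treatment are attached to loss to follow-up. The administrative-error branch follows with no timing of its own. The natural reading is that it applies whenever the error is found, but the sentence is loosely drafted and does not say so outright.

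**Step 2: can a treated patient be found ineligible?** Yes, by one route that the protocol itself opens. A non-operative patient may start treatment, have the DEXA later, and prove to have a femoral-neck T-score below the limit in 1.1. This route does not lead to an operated patient, because DEXA must precede surgery. An operated patient could be affected only if a criterion was missed at screening and at the Project Manager's review.

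**Step 3: apply both rules.**

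| Case | Removal sentence | Four-condition rule |
|---|---|---|
| Randomized, non-operative, DEXA done after randomization, T-score below limit | Patient and all data removed, if treated as a missed exclusion | Condition 1 fails; not excluded |
| Observational patient, any criterion | Patient and all data removed | Condition 1 refers to a randomization that did not occur; undefined |
| Treated patient with prior fusion visible on the baseline film | Patient and all data removed | Conditions 1 and 2 met; excluded from the analysis if 3 and 4 also hold, with nothing said about deleting data |

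The first row gives opposite answers, the second has no defined answer, and in the third the rules differ on what happens to the data. The protocol does not say which prevails. The observational cohort is the larger one: 188 planned against 82 randomized (Protocol, Study Design Overview).

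**Step 4: is anything retained elsewhere?** No supplied text keeps the adverse events of removed patients.

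**Step 5: direction and size (illustration only).** Let x of n treated patients in an arm have an event.

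- Remove one patient with an event: (x − 1)/(n − 1), which is below x/n whenever x < n.
- Remove one without: x/(n − 1), which is above x/n whenever x > 0.
- If the removed patient had an event with probability p, the expected change is (x − pn)/(n(n − 1)). This is zero when p = x/n, that is, when discovery has nothing to do with the event.

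Take n = 41, the planned randomized arm (SAP 1.6.3). The documents give no event rate, so x is assumed.

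| Assumed events | All 41 | One with event removed | Two with event removed | One without event removed |
|---|---|---|---|---|
| 4 | 9.8% | 3/40 = 7.5% | 2/39 = 5.1% | 4/40 = 10.0% |
| 8 | 19.5% | 7/40 = 17.5% | 6/39 = 15.4% | 8/40 = 20.0% |
| 10 | 24.4% | 9/40 = 22.5% | 8/39 = 20.5% | 10/40 = 25.0% |
| 12 | 29.3% | 11/40 = 27.5% | 10/39 = 25.6% | 12/40 = 30.0% |

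Pooling the cohorts gives 41 + 94 = 135 planned patients per treatment (SAP 1.6.3). Losing one patient with an event then changes 33/135 = 24.4% to 32/134 = 23.9%.

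If k treated patients are removed and each has event probability p, the chance of losing at least one patient with an event is 1 − (1 − p)^k. This runs from 10% (k = 1, p = 0.10) to 94% (k = 4, p = 0.50). Both k and p are assumptions.

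**The case against.** The strongest reply is that the four conditions govern removal itself, since the sentence introducing them says that removal follows ICH guidelines. On that reading a removal prompted by a complication is largely barred. A disease first revealed by the complication is unlikely to have been measured before randomization. A work-up prompted by an event is not equal scrutiny. The cardiac, pulmonary, renal and metabolic exclusion rests on the surgical team's judgment, so its detection is not completely objective. The Project Manager's check and the DEXA requirement before surgery also make operated-then-ineligible patients rare. Finally, adverse-event forms may already have been filed, and manual sections that the protocol cites but that are not supplied may contain safety-reporting rules.

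Much of this stands. A reader might infer that the plan deletes the complications of operated patients and so biases surgical complication rates downwards. The documents do not support that as stated. They never say that removal applies after treatment, the conditions can be read as blocking harm-triggered removal, and several exclusions (prior fusion, congenital lumbar scoliosis, high-grade spondylolisthesis) can be discovered without any complication.

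The reply does not remove the conflict. Even if the conditions govern removal, a treated patient who meets all four would still leave with all study data. The conditions remain undefined for observational patients. The late-DEXA route is in the protocol's own text, and the Project Manager's check cannot see a result that does not yet exist.

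**Conclusion.** The point holds as a conflict and a gap in Protocol 1.3. The removal sentence is not limited to untreated patients, it differs in scope and consequence from the exclusion rule that follows, and no supplied text retains the adverse events of a treated patient later found ineligible. If the sentence is followed literally, those events leave both the safety summaries and Aim 2.

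The size is unknown and probably small. In an arm of 41, one removal of a patient with an event lowers the rate by about 2 percentage points; one removal of a patient without an event raises it by well under 1. Pooled over 135 patients, one lost event is worth about half a point. These figures rest on assumed event counts and removals. A systematic downward bias should be claimed only where the event led to the discovery.

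The conclusion assumes that the timing limit belongs only to loss to follow-up and that no unsupplied manual section retains the data.

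**What to change.** In Protocol 1.3, replace removal of the patient and all study data with wording to this effect: a patient found ineligible after entry keeps all data collected and continues in follow-up if willing. Then:

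- apply the four conditions to the efficacy analysis only;
- state how they work when the DEXA is done after randomization, and what replaces the randomization reference point in the observational cohort;
- state in the SAP that every patient who received a study intervention is counted in the adverse-event summaries and in the Aim 2 adverse-event analyses;
- list exclusions by cohort and arm, with the reason for each.

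The cost is a few sentences in the protocol and SAP and continued follow-up visits for what should be a handful of patients. Reported complication rates may be slightly less favourable. Data that have been kept can still be set aside in a sensitivity analysis, whereas deleted data may not be recoverable.

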## Adult Symptomatic Lumbar Scoliosis (ASLS) NIH R01 AR055176-01A2

---

included, it would be helpful for the surgical team to give a description of why the decision was made to include only one of the two curves.

If a consented patient is later not able to return to the original study center or a participating center for surgical intervention, *it is expected that the patient will continue in the study and participate as fully as possible.*

[figure not shown]
Surgical summary data will not be collected or posted to the database unless the surgery was performed by one of the participating investigators. If the surgery is not performed by a participating investigator, a Monitored Events report will be completed to reflect 1. SAE (Hospitalization) and if applicable, intervention cross over and 2. Discontinued treatment/Follow up continued.

All follow up data will be collected by mail and telephone contact. Sites will complete MD assessments by phone and follow up on any due diligence report reaching contact threshold. Sites should try to obtain copies of radiographic images annually.

Sites and patients will be reimbursed for 'long distance' follow up as outlined in the MOOP, Section 25.

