In the event that subjects do not return for a scheduled follow-up visit, or fail to return mailed questionnaires in a timely manner (within four weeks of mailing), site coordinators will contact subjects via telephone and/or e-mail. After two failed attempts, site coordinators will send a U.S. Postal Service certified letter to the subject's last known address. Address change service will be requested with all mailings. If certified mailings are returned undeliverable with no forwarding address, site coordinators will notify the PM, who will then conduct Internet searches and fee-based searches, such as ChoicePoint, to locate missing subjects.

Any patient deciding not to return to &/or continue treatment at the study will continue to be followed by mail and telephone, if the patient is willing. A monitored events report will be completed to document this change in patient and treatment status (Discontinued treatment/Follow up continued). Sites will mail QOLs to patients at interim and clinical follow up intervals. Site will follow up with patient if Due Diligence Report reaches contact threshold, to clarify any questionable patient information, &/or follow up on any questionnaires not returned. Site will ask patient to mail x-rays at annual milestones, as outlined in the protocol. Follow up MD assessments will only document treatments actually prescribed/recommended the Study PI (not MD from outside institutions).

**1.6 Project Manager (PM).** In addition to confirming appropriate participant study enrollment the PM will be responsible for tracking and monitoring productivity at all centers to further ensure complete and accurate data. It will be the responsibility of this individual to strive for 100% follow-up in both nonoperative and operative arms of the study.

The PM will have 24 hour/day access to the data collected and stored on study patients. The PM will query the database on a daily basis to monitor each site's productivity (enrollment and follow-up). Likewise, the sites will have access to the PM via alpha pager.

Responsibilities of PM:

- Develop an operations manual.
- Provide detailed training of site coordinators upon study initiation at start-up meetings and throughout the remainder of the study via conference calls and site visits. Conference calls with the PM and site coordinators will be held weekly until all sites are actively participating and comfortable with the study protocol, with decreasing frequency as study needs dictate.

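### Surgery by a non-participating surgeon loses the surgeon-completed record of perioperative adverse events, and its admission is logged as an SAE with no rule for tabulating it

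*Protocol*

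**What the plan says.** The closing text of Protocol 1.4.2 covers consented patients who cannot return to a participating center for surgery. It has four parts.

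- Surgical data: "Surgical summary data will not be collected or posted to the database unless the surgery was performed by one of the participating investigators".
- Event log: "a Monitored Events report will be completed to reflect 1. SAE (Hospitalization) and if applicable, intervention cross over and 2. Discontinued treatment/Follow up continued". Because crossover is entered only where it applies, the rule also reaches patients who were assigned to surgery, or chose it, and had it elsewhere.
- Follow-up: "All follow up data will be collected by mail and telephone contact".
- Physician assessment: "Sites will complete MD assessments by phone and follow up on any due diligence report reaching contact threshold". Sites are also to try to obtain copies of radiographs each year.

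Protocol 1.5.1 describes the Surgical Summary as completed by the surgeon at the time of the operation, and says of its content: "Equally important will be the reporting of any intra-operative adverse events, as well perioperative adverse events occurring prior to discharge".

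Two other adverse-event routes in Protocol 1.5.1 stay open. The Monitored Events form takes serious events, and unexpected but reasonably related ones, at clinical visits, and: "In addition, sites will complete this form as applicable with each patient contact, including telephone calls". The Patient Intervention Follow-Up says: "Any adverse events stemming from nonoperative or operative treatments will be recorded along with changes in health history".

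Adverse events are named as an outcome in both arms under Specific Aim 2, in the Protocol and the SAP. The SAP addendum of 8/29/12 assigns complications and severe adverse events to follow-up intervals by their distance from the intervention date.

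**The concern.** The rule acts on the same patient in two ways.

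First, the form that the surgeon completes for events in the operating room and before discharge is not used. Nothing replaces it: no section of either document asks for the outside operative report or discharge summary, although outside radiographs are sought. What happened in that hospital stay then reaches the database only if it comes out later, by questionnaire or telephone.

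Second, the operation itself is entered as a hospitalization SAE. No rule separates an admission whose only purpose was the operation from one with a complication. No rule says whether an in-center operation is logged or tabulated in the same way.

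At stake is the comparability of adverse-event summaries under Aim 2, between in-center and outside surgery and, through crossovers, between arms. Under intent-to-treat, a non-operative patient who crosses over to surgery elsewhere carries both the SAE entry and any unrecorded perioperative events into the non-operative arm.

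**Working it through.** The documents give no number of outside operations, no SAE rate and no perioperative complication rate, so there is no planned figure to reproduce. The check compares the texts and then shows the scale under stated assumptions.

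**Step 1. The two settings side by side**

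| Item | Participating investigator operates | Outside surgeon operates |
|---|---|---|
| Surgical Summary (1.5.1; 1.4.2) | Completed by the surgeon | Not collected |
| Operative and discharge records | Own center's surgery | No request stated |
| Later contact (1.5.2; 1.4.2) | Clinic visits plus mailings | Mail and telephone |
| Monitored Events, patient-reported events (1.5.1) | Continue | Continue |
| Admission entered as an SAE | Not stated | Yes (1.4.2) |

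The settings differ in one primary source of perioperative events and in one explicit SAE instruction. The remaining routes are common to both.

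**Step 2. Effect of the SAE entry on an arm's SAE proportion**

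- N = 41 per randomized arm (SAP 1.6.3).
- k = outside operations in that arm (assumed).
- Added proportion = k / N, if the entry is counted and these patients have no other SAE.

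| k | k / 41 | Added points |
|---|---|---|
| 1 | 1/41 | 2.4 |
| 2 | 2/41 | 4.9 |
| 4 | 4/41 | 9.8 |
| 8 | 8/41 | 19.5 |

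The SAP addendum of 1/17/13 reports that 63 patients were randomized. An even split gives 63/2 = 31.5 per arm, and one outside operation then adds 1/31.5 = 3.2 points. In the observational cohort, with 94 per group (SAP 1.6.3), it adds 1/94 = 1.1 points.

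**Step 3. Perioperative events missed**

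- p = proportion of operated patients with a perioperative complication (assumed 20% to 40%).
- s = share operated on outside (assumed 5% to 20%).
- c = share of those events recovered by other routes (unknown; 0, 0.5 and 1 shown).
- Missed, in points of all operated patients = p × s × (1 − c).

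| | c = 0 | c = 0.5 | c = 1 |
|---|---|---|---|
| p = 20%, s = 5% | 0.20 × 0.05 = 1.0 | 0.5 | 0 |
| p = 40%, s = 20% | 0.40 × 0.20 = 8.0 | 4.0 | 0 |

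The result runs from none to 8.0 points over these assumptions, and c, which the documents do not fix, decides where it falls.

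**Step 4. The two errors do not cancel**

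The SAE entry is made for every outside operation, whatever happened. The missed events depend on p and c. One is a fixed code and the other is variable, so the first cannot stand in for the second.

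**Step 5. Primary outcome**

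Questionnaires continue by mail, and intent-to-treat keeps the patient in the assigned group. Neither the missing form nor the SAE entry enters the SRS-QOL model.

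**The case against.** The strongest reply is that one source is lost, not adverse-event capture. Monitored Events reports, patient-reported events and physician assessments by telephone all continue. This stands: a reader might infer that perioperative complications of outside surgery are dropped, and the documents support only that they can be under-recorded. What the reply does not supply is an equivalent of the surgeon's own account. Monitored Events is limited to serious, or unexpected but related, events, and the patient is a weak source for what occurred in the operating room.

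Three further points limit the concern.

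- *The physician-assessment limit.* Protocol 1.5.3 says: "Follow up MD assessments will only document treatments actually prescribed/recommended the Study PI (not MD from outside institutions". A reader might take this as barring complications of outside surgery from the later assessments. It restricts which treatments are documented; it does not mention adverse events.
- *The SAE entry.* A reader might infer that a planned operation is falsely counted as a harm only when done outside. The documents do not go that far. They contain no SAE tabulation rule, and the Schedule of Events marks the Monitored Events form on the intervention day, so in-center admissions may be logged too. The entry is labelled as a hospitalization, so an analyst could separate it. The SAP's Aim 2 modelling text also concentrates on quality-of-life trends and sets out no SAE comparison. What remains is that no rule is stated.
- *The discontinued-treatment code.* A reader might infer that a patient who had the assigned surgery is recorded as untreated. The full label says that follow-up continues, and 1.5.3 uses it for patients who stop coming to, or stop treatment at, the study site. Crossover is logged separately. The label describes leaving study-site care, not absence of surgery.

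The restriction also has a rationale: 1.4.2 wants surgery at study centers for uniformity, and an outside surgeon has no study role. That supports flagging outside data. It does not support leaving perioperative safety information unrequested.

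**Conclusion.** The concern holds in a limited form. For outside surgery the plan removes the surgeon-completed source of intra-operative and pre-discharge adverse events and requests nothing in its place, so these events can be under-recorded relative to in-center surgery. It also enters the operation as a hospitalization SAE without separating the admission from a complication and without saying that both settings are tabulated alike. Adverse-event summaries under Aim 2 may therefore not be comparable.

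The size is open because the number of outside operations is not given. At 41 per arm, each adds about 2.4 points to its arm's SAE proportion, on two conditions: the entry is counted, and the patient has no other SAE. The share of events missed starts at zero and depends on recovery through the other routes; all rates used for it are assumptions. The intent-to-treat quality-of-life outcome is not affected. The change is worth making because it is cheap and, in arms this small, a few patients are visible.

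**What to change.** Amend the closing text of Protocol 1.4.2 in three places.

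1. Replace the exclusion of surgical data with a request, under the patient's release, for the outside operative report and discharge summary. Abstract perioperative adverse events from them and mark the data with an outside flag.
2. Record the operation and its date as treatment received, in addition to the existing crossover and discontinued-treatment entries.
3. Code the admission for the study operation separately from complications, and state that it is tabulated the same way for in-center and outside surgery.

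The cost is form wording and a records request for what are likely to be a few patients, made by sites already asked to seek outside radiographs. Records for past operations can be requested and coded before analysis. Outside records may be less complete; the flag makes that visible and allows those patients to be shown separately.
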